isometric contraction followed by blood-flow occlusion) Vs. a control condition (no isometric contraction nor blood flow occlusion), on H-reflex recruitment curve and V wave excitability (aim #1). Since the activation of group III/IV afferents can inhibit the corticospinal pathway (61) we hypothesize that the normalized maximal amplitude and the slope of the ascending limb of the H-recruitment curve will decrease with metaboreflex activation. Additionally, we intend to examine the acute impact of different exercise modalities (resistance, supramaximal and endurance) on nociception sensibility (by the application of a cold tolerance test and by determining pressure pain threshold) (aim #2). This will allow us to investigate the role of different acute exercise paradigms on possible metaboreflex desensitization in its relationship with altered neuromuscular responses at post-exercise time point (attenuated inhibition of H-reflex and V-wave amplitude during metaboreflex activation). Also, once past research has shown that muscle metaboreflex activation reduces the sensitivity of the baroreflex (68), we will measure arterial pressure (AP) and heart rate variability (HRV) during cold pain tolerance testing. Despite all exercise modalities could enhance reducing pain sensibility after exercise, we hypothesize that resistance and supramaximal exercise stimuli will enhance nociceptive tolerance via metaboreflex desensitization compared to that seen with endurance exercise (attenuated increase of AP and sympathetic component of HRV during cold pressor test). Finally, we intend to explore the impact of long-term resistance, supramaximal and endurance training on nociceptive sensibility, using the same tests of aim #2 (aim #3). We hypothesize that chronic EIH will be of greater magnitude after supramaximal and resistance exercise training vs. endurance training. In addition, we hypothesize that decreased nociception will be related with attenuated inhibition of H-reflex and V-wave amplitude and attenuated increase of AP and sympathetic component of HRV during metaboreflex activation after training and this will result in increased exercise performance via heightened H-reflex and V-wave excitability.

2. Research Plan and Methods

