2.2 Aim #2

2.2.1 Participants

The intervention study will enroll 24 participants ((G Power 3.0.10 software) to achieve 80% of correctly rejecting the null hypothesis, based on Jones et al., (2016) (11)). Eight participants will be randomly allocated to each exercise modality (i.e. resistance, supramaximal and endurance). Specific inclusion and exclusion criteria are discussed in subsection 2.4.1.

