2.3 Aim #3

2.3.1 Participants

We will recruit a total of 30 participants. Sample size is overestimated in order to allow us to accommodate an attrition rate of ~ 20% during follow up, once participants will only be eligible for final testing if they attain at least 85% of the training sessions, with the goal of allocating at least 8 participants to each of the three training groups (G Power 3.0.10 software; to achieve 80% of correctly reject the null hypothesis, based on Jones et al. 2014 (38)). Specific inclusion and exclusion criteria are discussed in

subsection 2.4.1

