2.4.13 Statistical analysis (aim #1, #2 and #3)

Normality will be verified through the Shapiro-Wilk test. Univariate ANOVAs will be used to explore differences in the impact of blood-flow occlusion vs. non-blood flow occlusion on each H-reflex and V-wave variable (aim #1). Repeated measures ANOVA will be computed to determine significant main effects for time (pre- vs. post-acute exercise), condition (resistance vs. supramaximal vs. endurance exercise) and time-by-condition interactions on pain tolerance/threshold/ratings, AP, HRV and H-

reflex parameters and V-wave amplitude with metaboreflex activation (aim #2). Repeated measures ANOVA will be computed to determine significant main effects for time (pre- vs. post training), condition (resistance vs. supramaximal vs. endurance training) and time-by-condition interactions on exercise performance, pain tolerance/threshold/ratings, AP, HRV, H-reflex parameters and V-wave amplitude with metaboreflex activation, and neuromuscular adaptations to training (aim #3). Correlations between the impact of exercise or training on pain tolerance/threshold/ratings and performance on H-reflex, V-wave, AP and HRV variables will also be explored. Significance level will be set at $p < 0.05$. All data will be treated using SPSS 25.0 for statistical analysis.

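### Section 2.4.13 does not say whether the pain–reflex and performance correlations are pooled, run by group or adjusted for modality; pooled correlations can be confounded by modality, and separate groups of 8 can detect only very large correlations.

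*Combined protocol and SAP*

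**What the plan says.** Section 1.3 (Purpose) states a hypothesis about a relation between outcomes. For training, "we hypothesize that decreased nociception will be related with attenuated inhibition of H-reflex and V-wave amplitude", together with a smaller rise in arterial pressure (AP) and sympathetic heart rate variability (HRV), and a consequent gain in performance.

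The analysis that serves this hypothesis is in section 2.4.13: "Correlations between the impact of exercise or training on pain tolerance/threshold/ratings and performance on H-reflex, V-wave, AP and HRV variables will also be explored". The next sentence reads "Significance level will be set at $p < 0.05". No coefficient, grouping, partial correlation or stratification is given. Modality enters section 2.4.13 only as a factor in the repeated measures ANOVAs, for example "condition (resistance vs. supramaximal vs. endurance training) and time-by-condition interactions on exercise performance".

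The data come from three parallel modality groups. In aim #2 (section 2.2.1), "Eight participants will be randomly allocated to each exercise modality", giving 24 in all. In aim #3 (section 2.3.1), "We will recruit a total of 30 participants", with the aim of at least 8 in each training group after dropout.

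**The concern.** The ANOVAs take one outcome at a time, so they cannot test a relation between two outcomes. The correlations are the only named analysis that can, and describing them as exploratory does not change what they will be used to support.

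The three groups receive different exercise, and the protocol expects them to respond differently. When two change scores both differ in mean between groups, a correlation over all participants mixes that between-group pattern with the association among people who did the same exercise. Section 1.1 lists several possible routes to hypoalgesia (opioid, cannabinoid, cardiovascular, central and peripheral). Modality could therefore move pain and reflexes by separate routes and still leave a pooled correlation that reads as support for the proposed mechanism. A real association could equally be masked.

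The other plain reading, a correlation within each modality, avoids this bias but has only about 8 observations per estimate.

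**Working it through.** **The plan's own figure.** Aim #3 needs 3 × 8 = 24 evaluable participants and wants to "accommodate an attrition rate of ~ 20% during follow up". 24 / (1 − 0.20) = 30, which matches the plan. The 8 per group cannot be reproduced, because section 2.2.1 gives the target, "to achieve 80% of correctly rejecting the null hypothesis", without an effect size or SD, and section 2.3.1 gives neither for aim #3. No stated figure covers the correlations.

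**Critical correlations** (two-sided 0.05 assumed, as the plan does not state sidedness), from r = t / √(t² + df):
- Pooled, N = 24, df = 22: |r| = 0.40
- Adjusted for three modalities, N = 24, df = 24 − 3 − 1 = 20: |r| = 0.42
- One group of 8, df = 6: |r| = 0.71

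**Bias if pooled.** Assume equal groups, unit SD within group, true within-modality correlation 0, and a shift of d SD in both change scores in two of the three groups. The between-group variance of each score, and their between-group covariance, is d² × (2/3) × (1/3) = 2d²/9. The pooled correlation is then

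r = (2d²/9) / (1 + 2d²/9).

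At d = 1 this is 0.222 / 1.222 = 0.18; at d = 1.5 it is 0.5 / 1.5 = 0.33. Simulation with 100,000 replicates per setting gives:

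| d (SD, assumed) | r by formula | Pooled false positives, 8 per group | Pooled false positives, 10 per group |
|---|---|---|---|
| 0 | 0.00 | 4.9% | 4.9% |
| 0.5 | 0.05 | 5.7% | 5.8% |
| 1.0 | 0.18 | 13.8% | 16.5% |
| 1.5 | 0.33 | 38.1% | 47.3% |
| 2.0 | 0.47 | 72.5% | 82.6% |

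The modality-adjusted correlation stays at 4.9% to 5.1% with mean r of 0.00 in every row.

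**Other shift patterns, 8 per group.**
- Only one variable differs between groups (1.5 SD): 5.1% false positives, so no inflation.
- Pain shifted in resistance and supramaximal, the reflex measure shifted in supramaximal and endurance: the covariance is 1/3 − (2/3)(2/3) = −1/9 in units of d², so r = −0.09 at 1 SD and −0.17 at 1.5 SD, with 6.9% and 11.2% significant, nearly all in the direction opposite to the hypothesis.
- Pain shifted in resistance and supramaximal, the reflex measure shifted in resistance only: r = +0.09 and +0.17, with 6.8% and 11.4%.
- Masking, with a true within-modality r of 0.5 and opposite shifts of 1 SD: pooled mean r falls to 0.21 and power to 15.5%, against 68.6% when adjusted.

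**Performance in aim #3.** Sections 2.3.4.1 to 2.3.4.3 give each training group its own test: knee-extension torque and time holding 40% of maximum for resistance, treadmill distance for endurance, and number of 30 s bouts for supramaximal. Raw changes on these scales cannot be combined in one correlation. This needs no assumed effect size.

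**The case against.** The plan never says that it pools. A reader might infer from the bare sentence that a simple correlation over all participants is intended, but section 2.4.13 is equally compatible with correlations by group. What is shown is a missing specification. This stands.

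A reader might also infer that the correlations would usually come out significant merely because the modalities differ. The figures do not support that. The excess is negligible at 0.5 SD, material from about 1 SD, and above half only at 2.0 SD in both variables, and the documents give nothing from which to judge whether such shifts are likely. This also stands.

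The aligned shift is only partly in the protocol. Section 1.3 orders the modalities for pain in aims #2 and #3, and for AP and sympathetic HRV in aim #2. For H-reflex and V-wave an ordering is only implied, through metaboreflex desensitization. Section 1.2 cites H-reflex gains after endurance and Wingate training and V-wave gains after resistance training, a different pattern that would give smaller or reversed bias. Those are ordinary training adaptations, not inhibition during occlusion, so they do not remove the concern. They do show that its direction and size depend on the pattern assumed.

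Finally, it is tempting to say that pooling hides a link within individuals. Each participant gives one change score per variable, so neither a pooled nor an adjusted correlation measures that. What adjustment recovers is association between individuals within a modality.

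**Conclusion.** The concern holds as a gap in specification with a clear better choice. The hypothesis in section 1.3 that links pain, reflex, cardiovascular and performance changes has one sentence of analysis, and that sentence leaves open two readings that are both poor: a pooled correlation open to confounding by modality, and separate correlations in groups of 8 that need |r| of at least 0.71.

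The false-positive rates of about 6%, 14%, 38% and 73% rest on assumptions: normal data, equal groups, a two-sided 5% test, no within-modality correlation, and equal shifts of 0.5 to 2.0 SD in both variables in the same two groups. They show what could happen and do not predict what will. The incompatible performance scales in aim #3 rest on no such assumption. As the correlations are described as exploratory and the remedy is wording, this is a worthwhile improvement and not a threat to the ANOVA comparisons.

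**What to change.** In section 2.4.13:
- Specify correlations of the change scores adjusted for modality, either as partial correlations or as a common within-modality slope from ANCOVA with a group term. Report confidence intervals, and show the within-group estimates descriptively.
- Keep all the pairs that sections 1.3 and 2.4.13 name, including pressure pain threshold and performance. Narrowing the list to pain tolerance would drop outcomes that the hypotheses cover.
- For aim #3, standardise performance change within each training group before it enters any correlation.
- Label the results exploratory.

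The cost is two degrees of freedom. At N = 24 critical |r| rises from 0.40 to 0.42. Without group shifts, power falls from 72.9% to 68.9% for a true r of 0.5, and from 89.9% to 87.0% for 0.6. No further participants, visits or measurements are needed.

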2.4.14 Final study procedures (aim #1, #2 and #3)

All data will be compiled in Neuromuscular Research Laboratory private cloud. We will ensure the participants confidentiality by attributing a code number to each person. Only the main researcher and his supervisor will have access to the data, and always through the code numbers. All participants will have access to their results via an individual report.

